1.0 Lines of responsibility and accountability

- 1.1 Up until the point at which a participant has undertaken their eligibility confirmation assessment with King's contracted Assistant Psychologists (AP) and before their details are forwarded to Inspire on randomisation and for therapy appointments to be allocated, the participant's GP holds responsibility and accountability for the participant's mental health and wellbeing and this includes their safety.
- 1.2 For those participants randomised to receive FIRST therapy immediately (the Intervention arm) from the point at which the participant's details are handed over to Inspire to arrange their therapy sessions through to the point of discharge, Inspire have responsibility and clinical governance accountability for the participant's mental health and wellbeing and including their own safety and where relevant the safety of others and including the safeguarding of children and vulnerable adults.
- 1.3 From the point of discharge from Inspire therapy to the point of 52-week follow-up or withdrawal from the trial, the Intervention participant's GP holds responsibility and accountability for the participant's mental health and wellbeing and this includes their safety.
- 1.4 For those participants randomised to receive FIRST therapy in 20 weeks (the Control arm) up until therapy begins the participant's GP continues to hold responsibility and accountability. At the point therapy delivery with Inspire begins at 20-weeks until the point of discharge approximately four weeks' later, Inspire have responsibility and clinical governance accountability. Once therapy is completed for these participants, they are discharged from Inspire and their time in the study is complete. Responsibility for the participant's mental health and wellbeing returns to their GP.
- 1.5 Participant safety will be a standing agenda item on every fortnightly core research team sub-group meeting.
- 1.6 Data Monitoring and Ethics Committee (DMEC) will meet once during the Proof of Concept trial and four times during the full trial and comprises two trauma experts and an independent statistician. The DMEC terms of reference will operate according to the King's Clinical Trials Unit Standard Operating Procedures. The research team will report any participant safety issues to the DMEC within 48 hours of each fortnightly core research team sub-group meeting.

2.0 Definitions related of safety

- 2.1 Mental health safety symptom severity, deterioration is assessed using the PCL-5 selfreport screening questionnaire completed by the participant at the beginning of every therapy session until discharge. Any existing or emergent safeguarding and or vulnerable adult concern will be assessed and monitored at each session with proportionate action taken in accordance with legislative reporting requirements.
- 2.2 Mental health safety is assessed using the PCL-5 and PHQ-9 (question 9) self-report screening questionnaires completed by the participant at the following time points following FIRST therapy discharge (intervention arm), or while awaiting therapy commencement at 20-weeks (control arm): 6 weeks post randomisation, 12 weeks post randomisation, 20 weeks post randomisation and 52 weeks post randomisation (for those in the intervention arm).
 - 2.2.1 The named researcher will review all incoming follow up PCL-5 and PHQ-9 scores within 72 hrs of receipt.
 - 2.2.2 If PHQ9, Q.9 (risk of self-harm) is scored 1-3 this will trigger a safety contact email correspondence from the assessors (see 4.0).
- 2.3 PTSD Adverse Events are defined as a ≥10 point rise in the self-report PCL-5 since the previous therapy session or a 15 point rise from baseline or the maximum score of 80 being reached and/or relapse into alcohol and/or substance misuse at a hazardous level which integrated with the clinical judgement of the treating therapist will determine the action taken.
- 2.4 The risk of Self-Harm Adverse Event is defined as when the research team has been unable to make contact with the participant (see 4.5) on three separate occasions and contact is made from the research team to the participant's GP.
- 2.5 PTSD Serious Adverse Events are defined as hospital admission for mental ill-health, self-harm, suicide and attempted or completed suicide.

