Intervention (Description, frequency, details of delivery)	FIRST is a brief intervention delivered in 3 to 4 x 90-120 minute sessions by a FIRST therapist via videocall. FIRST rewrites the emotional elements of the memory. FIRST therapy will be delivered over a minimum of three days and a maximum of four weeks. The two factors determining this are a) there must be one sleep cycle between each therapy session and b) scheduling of therapy sessions for the participant and the therapist. The FIRST protocol incorporates 18 steps in five stages: a) Pre- randomisation assessment by DES; b) Priming process; c) Desensitisation process through dissociation; d) Undoing of trauma memory through reversed imagery; e) Reconsolidation. Therapy sessions will be delivered remotely, and our therapy delivery and clinical governance partner and collaborator is Inspire; a mental health charity located in Northern Ireland (https://www.inspirewellbeing.org/) who delivered all therapies remotely in the feasibility trial. Inspire therapists are experienced in working remotely with cross-UK and Republic of Ireland military veterans since online mental health assessment and therapy became mainstream therapeutic provision during the COVID-19 pandemic. For an efficacy trial this third sector organisation offers a more ideal setting for the following reasons: a) the flow of participants through the trial is controllable because there are many fewer competing interests than within the NHS; b) Inspire, due to their Northern Ireland location, have considerable expertise in working with military veterans and other populations with occupationally-related PTSD; and c) they have robust clinical governance procedures which are adaptable to being supplemented with FIRST		

	therapy-specific clinical supervision.
Comparator Intervention:	Waiting List
Maximum Duration Of Treatment Of A Subject:	Four weeks
Version And Date Of Final Protocol:	V1.0 23-04-24
Version And Date Of Protocol Amendments:	

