8.6 Planned interventions and delivery

The experimental therapy, FIRST, uses non-propriety, copyright free, techniques with the intellectual property shared between [name] and King's College London. All participants will be randomly allocated to receive FIRST within three weeks of randomisation or to a waiting list group who will receive FIRST 20 weeks following randomisation.

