10.5 Randomisation and stratification

King's College London Clinical Trials Unit (KCTU) will provide a computer randomisation service. Stratification will be undertaken on diagnosis of PTSD or CPTSD, age and sex. Randomisation will take place after the eligibility confirmation assessment and once baseline data has been completed. Participants will be randomised to the intervention arm where they will receive therapy immediately or to the waiting list control.

Only three members of the research team will be unmasked: the lead clinical provider, the safety monitoring researcher and the trial statistician (the senior statistician will remain masked). All those entering data will be masked to treatment group. For participants randomised to the intervention group, therapy will commence within three weeks. If participant holidays are arranged, randomisation will be delayed ensuring this timeline can be maintained.

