14.1 Adverse events

PTSD Adverse Events are defined as a \geq 10 point rise in the self-report PCL-5 since the previous therapy session or a 15 point rise from baseline or the maximum score of 80 being reached and/or relapse into alcohol and/or substance misuse at a hazardous level which integrated with the clinical judgement of the treating therapist will determine the action taken.

Self-harm adverse events are defined as responding 1 or above on the PHQ-9, question 9 and

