14.3 Care escalation procedures

If the participant is in therapy, Inspire will hold responsibility and clinical governance accountability for the participant's mental health and wellbeing, including their own safety and where relevant the safety of others and including the safeguarding of children and vulnerable adults. If at point of referral or during the course of treatment, Inspire therapists become concerned about the welfare of any participant or immediate family member they will escalate their concerns through Inspire's standardised risk assessment, escalation, management and safeguarding policies and procedures. Where necessary they will contact the participant's GP to mobilise referral to crisis response, NHS primary or secondary care. Likewise, if a safeguarding and vulnerable adults concern is identified this will be escalated, acted on and reported to the relevant statutory body – safeguarding team.

Before the participant is referred to Inspire and after discharge, the participant's GP holds responsibility and accountability for the participant's mental health and wellbeing and this includes their safety. If the participant scores on the PCL-5 indicate an adverse event, the unmasked researcher responsible for participant safety will make contact with the participant within six hours of noting the rise in score and encourage them to contact their GP and/or case worker. They will advise the participant that they will need to contact the participants GP and/or case worker to alert them to the rise in PTSD symptoms. The research team will review all incoming follow-up PCL-5 and PHQ-9 scores within 72 hours of receipt.

All AE will be recorded and reported to the study PI within 72 hours and will be discussed at the biweekly research core-team sub-group meeting. A report will be included in the TSC reporting for review.

A Serious Adverse Event that occurs following discharge from Inspire but whilst in the trial will be investigated by one of the study's senior investigators (i.e. [name] or [name]) using Inspire's SAE investigational policies and procedures. The investigational report will be submitted to the DMEC chair.

The DMEC chair will be notified within 24 hours of the research team being notified of all serious adverse events.

All AE and SAE and the clinical and research team actions will be logged in the Trial Management File.

15 Ethics and regulatory approvals

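### A permitted therapy course can still be open at the week-6 PHQ-9, and section 4.0 of the safeguarding protocol has no step that tells Inspire of a positive question 9 answer

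*Protocol*

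**What the plan says.** **Start of therapy.** Protocol section 8.6: "All participants will be randomly allocated to receive FIRST within three weeks of randomisation". Section 10.5 agrees: "For participants randomised to the intervention group, therapy will commence within three weeks".

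**Length of therapy.** Protocol section 1.6, repeated in 8.7: "FIRST therapy will be delivered over a minimum of three days and a maximum of four weeks".

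**Follow-up safety measures.** Appendix 1, item 2.2 lists the PCL-5 and PHQ-9 time points as "following FIRST therapy discharge (intervention arm), or while awaiting therapy commencement at 20-weeks (control arm): 6 weeks post randomisation", then 12, 20 and (intervention arm) 52 weeks. Therapy sessions themselves carry the PCL-5 but not the PHQ-9 (section 14; Table 7; Appendix 1, items 2.1 and 5.1.1).

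**Accountability.** Appendix 1, item 1.2, for the intervention arm, from handover "through to the point of discharge, Inspire have responsibility and clinical governance accountability". Section 14.3: "If the participant is in therapy, Inspire will hold responsibility and clinical governance accountability". Before referral to Inspire and after discharge, the GP is accountable.

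**Response to question 9.** Appendix 1, items 4.1 to 4.5: on a score of 1-3 the assessor contacts the participant and suggests the GP. With no reply in 24 hours a second message goes out, then a third. Only if that too is unanswered are the GP and a senior investigator told. Inspire and the treating therapist are not named.

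**Masking.** Section 10.5: "Only three members of the research team will be unmasked: the lead clinical provider, the safety monitoring researcher and the trial statistician".

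**The concern.** Item 2.2 reads as though every intervention-arm participant has left therapy by week 6, and section 4.0 is written on the same footing: its only clinician is the GP. For someone still in therapy at week 6, the party accountable on that date is Inspire.

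The therapist has no other stated way to learn of the answer. The PHQ-9 is not taken in sessions. Item 5.1 starts from the therapist's own concern. The weekly check in item 3.1.3 carries information from the therapy database to the research team, not back. If the score counts as an adverse event under section 14.1, section 14.3 adds the PI, the core team and the TSC, and again not Inspire. The definition there, "Self-harm adverse events are defined as responding 1 or above on the PHQ-9, question 9 and", breaks off in the text available, so nothing is built on it.

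What is at stake is a narrow safety matter. A therapist could run a further session, in a therapy with a stage in which the trauma memory is re-experienced (Table 3), without knowing that the participant has just reported thoughts of self-harm to the same trial.

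**Working it through.** The protocol gives no figure of its own here, so this is a timeline check. All times are counted from randomisation.

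**Inputs**
- Latest start S: 3 weeks (sections 8.6, 10.5).
- Course length D: 3 days (3/7 week) to 4 weeks (sections 1.6, 8.7).
- Assessment: week 6, day 42 (Appendix 1, item 2.2).
- Size of FIRST arm: 215/2 = 107.5 (section 10.6, 1:1 allocation).

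**Step 1: can the two overlap?** Latest end = 3 + 4 = 7 weeks, day 49. That is 49 - 42 = 7 days after the assessment.

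**Step 2: who overlaps?** S + D > 6 with S ≤ 3 and D ≤ 4 requires S > 2 and D > 3: a start in the third week and a course longer than three weeks. A start at week 2 with four weeks, or at week 3 with three weeks, ends exactly at week 6. If the last session is taken as discharge, everyone in the overlap has at least one session left.

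**Step 3: what share?** The protocol gives no distribution of starts or durations for FIRST, so these are assumptions. With S and D independent and uniform, the overlap is a triangle with both legs 1 week and area 0.5. The share is 0.5 divided by (range of S × range of D), where 4 - 3/7 = 3.571.

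| Starts (weeks) | Courses (weeks) | Calculation | Share | People of 107.5 |
|---|---|---|---|---|
| all by 2 | any permitted | none | 0% | 0 |
| any permitted | all 3 or less | none | 0% | 0 |
| 0-3 | 3/7-4 | 0.5/(3 × 3.571) | 4.7% | 5.0 |
| 1-3 | 3/7-4 | 0.5/(2 × 3.571) | 7.0% | 7.5 |
| 0-3 | 2-4 | 0.5/(3 × 2) | 8.3% | 9.0 |
| 2-3 | 3/7-4 | 0.5/(1 × 3.571) | 14.0% | 15.1 |
| 2-3 | 2-4 | 0.5/(1 × 2) | 25.0% | 26.9 |

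The 2-4 week rows are centred on the mean duration of three weeks that section 5.5 reports for earlier reconsolidation studies. The table counts people in therapy at week 6, not alerts. No question 9 rate is given, so alerts cannot be estimated.

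**Step 4: when does the GP hear?** Three messages with 24-hour waits make about 3 days after the score is noticed. Review may take up to 72 hours (item 2.2.1), so GP contact falls about 3 to 6 days after receipt. For a form received on day 42 that is day 45 to day 48. A participant who replies triggers no stated contact with any clinician.

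**The case against.** Several points on the other side are sound.

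- **The GP is not the first stop.** A reader might infer that the alert goes straight to the wrong clinician. It does not: the participant is contacted first. By the time the GP is reached, most courses in the overlap have ended and the GP is accountable again. With immediate review, therapy is still open beyond day 45 in (4/7)² = 33% of the overlap. In the first uniform case that is 4.7% × 0.33 = 1.5%, or about 1.6 people, before restricting to those who score 1-3 and leave three messages unanswered. This stands. The remaining point is that the therapist is not told in the meantime.
- **Masking.** A reader might infer that a masked assessor cannot know that Inspire is accountable. The protocol does not say whether the assessor handling question 9 is masked. Item 2.2.1 gives score review to a named researcher, and an unmasked safety researcher exists. Masked or not, section 4.0 gives no instruction to inform Inspire.
- **Item 2.2 wording.** A reader might infer that an assessment could be moved or skipped. The same sentence fixes it at 6 weeks after randomisation, as does Table 7, so the phrase alone changes no assessment.
- **Incomplete text.** The section 14.1 definition breaks off, the Appendix 2 flow diagram is not reproduced, and Inspire's own policies are not in the protocol. The claim is therefore limited to the steps stated in section 4.0.
- **Mitigation.** Each session includes the PCL-5 and a check for safeguarding concerns (2.1), therapists can escalate (5.1), the Contact Card lists Inspire's helpline where appropriate (3.1), and the opening of Appendix 1 promises liaison with clinical teams. These reduce the risk, but none of them passes the answer to the therapist.
- **Rarity.** Section 4.4 describes the therapy as immediate, and early starts would bring the share to zero. That supports a low severity. It does not close the gap.

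**Conclusion.** The point holds as a minor gap in the safeguarding protocol. The overlap follows from the protocol's own limits: week 7 is permitted and the PHQ-9 is at week 6. For anyone in that overlap, following section 4.0 exactly leaves the accountable provider untold of a question 9 score of 1-3 while a session remains, within at most 7 days.

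The share affected rests wholly on assumed schedules and on treating the last session as discharge. The figures in the table are illustrations and not bounds, and the number of alerts is unknown and could be very small. Item 5.2 has the same omission for PCL-5 rises at follow-up, but the PCL-5 taken at each session largely covers it. Nothing here touches the 20-week treatment comparison.

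**What to change.** In Appendix 1:

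1. **Section 4.0.** Add that the assessor passes every question 9 alert, from either arm, to the unmasked safety researcher. That researcher informs Inspire the same day if the participant is under its care (intervention arm, handed over and not yet discharged). Keep the participant contact and GP steps as they are. Waiting-list participants stay on the GP route until their therapy begins (item 1.4).
2. **Item 5.2.** Add the same notice to Inspire. The unblinded researcher already acts at this step.
3. **Item 2.2.** As a consequential edit, drop the words that place the intervention-arm assessments after discharge, so that they are defined by time since randomisation alone.

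Because alerts from both arms take the same route, passing one on reveals nothing about allocation, whether or not the assessor is masked. The cost is two added sentences and one deleted phrase, with no new staff, assessments or data.

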8.10.2 Comparison intervention

Participants randomised to the waiting list control (WL) group can continue with any ongoing care or newly engage with usual care pathways available in NHS veterans' services and charities for non-PTSD mental health concerns. Participants will be offered FIRST therapy following the completion of data collection at 20 weeks post randomisation. They will be informed of the appointment date/time for FIRST therapy commencement at the point of randomisation. Safety data is collected at six and 12 weeks and our well-performing feasibility study safety protocol will ensure that any escalation of symptoms in waiting list participants will be detected and recorded as

an adverse event (Appendix 1).

9 Phase 1: Proof of concept study

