22.1 Appendix 1: Participant safeguarding protocol

The safety of potential and actual participants is the greatest ethical concern. Our feasibility safety protocol performed well and we have strengthened it to address the safety needs of ineligible participants and participants in the Waiting List (WL) arm of the study.

This Safety Protocol follows the best practice, professional guidelines, and local NHS policies for monitoring mental state and risk throughout the participants' involvement in the trial and will be facilitated by close liaison with clinical teams. The safety of the FIRST psychotherapy intervention will be monitored closely during therapy sessions and through regular contact with the participant's clinical team or GP.

The following comprises our safety protocol for all participants in the trial: those randomised to receive the Intervention immediately, those who are placed on the WL to receive FIRST in 20 weeks' time and those that withdraw. It addresses lines of responsibility and accountability, definitions relating to safety, escalation and safeguarding procedures in the event of notable clinical deterioration with or without an escalation in risk, alongside ensuring the safe and effective management of participants who are ineligible to enter the trial.

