5.0 Care escalation procedures in the case of adverse event

- 5.1 If at point of referral or during the course of treatment, Inspire therapists become concerned about the welfare of any participant or immediate family member they will escalate their concerns through Inspire's standardised risk assessment, escalation, management and safeguarding policies and procedures. Where necessary they will contact the participant's GP to mobilise referral to crisis response, NHS primary or secondary care. Likewise, if a safeguarding and vulnerable adults concern is identified this will be escalated, acted on and reported to the relevant statutory body safeguarding team.
 - 5.1.1 The PCL- 5 will be completed at each therapy session. If ≥10 point rise in PCL-5 score occurs since the previous therapy session, or 15-point rise from baseline, or the maximum score of 80 is recorded on the PCL-5, they will use their clinical judgement to assess whether escalation is appropriate.
 - 5.1.2 Any ≥10 point rise in PCL-5 score that occurs since the previous therapy session, or 15-point rise from baseline, or the maximum score of 80 recorded on the PCL-5, will be detected by the unblinded member of the research team (investigator [name]) who will inform the DMEC chair within three working days.
- 5.2 If a participant's PCL-5 score rises by ≥10 points from the previous follow up, or 15point rise from baseline, or the maximum score of 80 is recorded on the PCL5, the unblinded researcher (investigator [name]) will make contact with the participant within six hours of noting the rise in score and encourage them to contact their GP and/or their case worker. They will advise the participant that the researcher will need to contact the participant's case worker (or GP if no case worker) to alert them to the rise in PTSD symptoms.

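### During the 20-week wait, waiting-list participants cannot meet the 10-point PCL-5 limb of the adverse-event definition, although Appendix 1 item 5.2 escalates such a rise

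*Protocol*

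**What the plan says.** **Definition.** Appendix 1 item 2.3 has the PTSD adverse event "defined as a ≥10 point rise in the self-report PCL-5 since the previous therapy session or a 15 point rise from baseline", or a score of 80, and/or a hazardous relapse into alcohol or substance misuse. The treating therapist's judgement enters into the action taken. Section 14.1 uses the same reference point: "point rise in the self-report PCL-5 since the previous therapy session or a 15 point rise from baseline".

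**Who has a therapy session.** In the waiting-list arm, "Participants will be offered FIRST therapy following the completion of data collection at 20 weeks post randomisation" (8.10.2). Until then the PCL-5 is taken at baseline and weeks 6, 12 and 20 (Appendix 1 item 2.2). In the treated arm it is also "completed by the participant at the beginning of every therapy session until discharge" (item 2.1).

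**Scope.** Appendix 1 opens with "The following comprises our safety protocol for all participants in the trial" and names the waiting list among them.

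**Escalation.** Section 5.0 of Appendix 1 is headed as the procedure for adverse events. Its item 5.2 applies when a "PCL-5 score rises by ≥10 points from the previous follow up", with the same 15-point and score-80 alternatives, and requires contact with the participant within six hours. Section 14.3 attaches the same six-hour contact to PCL-5 scores that point to an adverse event.

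**Commitment to the waiting list.** Section 8.10.2 says that "any escalation of symptoms in waiting list participants will be detected and recorded as" an adverse event, and refers to Appendix 1.

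**The concern.** The definition measures the 10-point rise from the last therapy session. The escalation rule for follow-up visits measures it from the last follow-up. During the randomised comparison a waiting-list participant has follow-ups but no sessions, so the two rules part company in that arm.

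What is at stake is classification and reporting. Section 14.3 ties several steps to the event being an adverse event: recording it, reporting it to the principal investigator within 72 hours, discussing it at the fortnightly meeting, and including it in the steering committee's report. Item 5.2 requires contact but none of these steps. Section 10.7 also names waiting-list symptom escalation as something the internal pilot will monitor. If that is done by counting adverse events, the count depends on which sentence is followed.

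**Working it through.** No figure in the protocol needs reproducing; this is a comparison of two rules.

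**The rules.** Let y0 be the baseline PCL-5, yt the current score, ys the score at the previous therapy session and yp the score at the previous follow-up.

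- Definition (14.1, item 2.3): yt − ys ≥ 10, or yt − y0 ≥ 15, or yt = 80.
- Follow-up escalation (item 5.2): yt − yp ≥ 10, or yt − y0 ≥ 15, or yt = 80.

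For the waiting list, ys does not exist at weeks 6, 12 or 20, so the PCL-5 part of the definition reduces to its last two limbs. The gap is every score with yt − yp ≥ 10, yt − y0 ≤ 14 and yt < 80.

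**Waiting-list examples.**

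| Baseline / previous / current | Rise from previous | Rise from baseline | Item 5.2 | 14.1 and item 2.3 |
|---|---|---|---|---|
| 50 / 50 / 62 | +12 | +12 | escalated | not an adverse event |
| 57 / 47 / 60 | +13 | +3 | escalated | not an adverse event |
| 57 / 40 / 71 | +31 | +14 | escalated | not an adverse event |
| 57 / 57 / 72 | +15 | +15 | escalated | adverse event |

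The same rise from 50 to 62 between two therapy sessions is an adverse event.

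**Intervention arm after discharge.** Here ys exists as the last-session score, so the gap is partial. Take baseline 57, week 12 at 35 and week 20 at 47. The rise from the previous follow-up is 47 − 35 = 12, so item 5.2 applies. With a last-session score of 35 the definition is met (47 − 35 = 12). With 45 it is not (47 − 45 = 2, and 47 − 57 = −10 from baseline).

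**How often: an illustration only.** The protocol gives no between-visit correlation and no waiting-list data.

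- From the protocol: mean baseline 57 in the feasibility trial (5.5), screening score above 32 (8.3.3), and 86 per arm after 20% loss (10.6: 215 × 0.8 = 172; 172 / 2 = 86).
- Assumed: SD 14 to 20 (10.6 uses 20), correlation 0.5 to 0.9 and equal between all visits, normal scores rounded and clipped to 0–80, and linear mean change of 0 or −8 by week 20.
- Discordant means at least one rise of 10 or more from the previous follow-up, with no score 15 or more above baseline and no 80 at any follow-up.

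Results over 40 scenarios of 400,000 simulated participants each:

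| Quantity | Weeks 12 and 20 only | Also week 6 against baseline |
|---|---|---|
| Discordant, share of arm | 0.046–0.297 | 0.067–0.334 |
| Multiplied by 86 | 4.0–25.5 | 5.8–28.7 |
| Of these, less than 10 above baseline at the trigger | 78–94% | 57–78% |
| Of these, at or below baseline at the trigger | 18–61% | 13–54% |
| Share of arm 10–14 above baseline | 0.3–5.6% (0–5 of 86) | 2–11% (2–9 of 86) |

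A cruder model (flat mean of 57, independent scores, SD of change 8 to 16, week 6 compared with baseline) gave 26–35%. The width of these ranges shows how far the count depends on the assumptions.

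**The case against.** The strongest reply is that a contact threshold may reasonably be wider than a reporting definition. The heading of section 5.0 does not turn everything beneath it into an adverse event. Item 5.1 starts with "If at point of referral or during the course of treatment, Inspire therapists become concerned about the welfare of any participant", which is plainly not an adverse event under item 2.3. Section 8.10.2 names no 10-point figure, so it can be read as relying on the definition in Appendix 1, whose 15-point and score-80 limbs do reach the waiting list.

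Part of this stands. The heading alone would prove little, and 8.10.2 does not promise to record every 10-point rise. But 14.3 attaches to an adverse event the same six-hour contact that 5.2 attaches to its triggers. That suggests the authors regarded those triggers as adverse events and left the follow-up comparator out of the definition. Nothing in the protocol says that 5.2 is meant to be wider.

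A reader might infer more than the text supports:

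- *The limb never applies to the waiting list.* It does once they start FIRST after week 20, because they are then scored at each session (Appendix 1 items 1.4 and 2.1).
- *Deterioration on the waiting list goes unnoticed.* Follow-up scores are reviewed within 72 hours, 5.2 requires contact, and safety issues reach the data monitoring committee within 48 hours of each fortnightly meeting (Appendix 1 item 1.6). That committee has unmasked access (12.4).
- *A progression decision or the trial comparison is affected.* Table 6 has no safety criterion, and the protocol sets out no between-arm comparison of adverse events.

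**Conclusion.** The inconsistency is real and follows from the wording alone. While they wait, waiting-list participants cannot meet the 10-point limb, although a 10-point rise between follow-ups is escalated in the section on adverse events. Followed literally, such a rise is acted on but is not an adverse event unless another limb is met. Discharged intervention participants are affected in part.

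Severity is minor. The consequence is the label and the investigator and steering-committee reporting that follow from it; participant contact is not lost. The illustrative 5–30% of the arm (7–33% with week 6) rests on assumed correlations, SDs and drift, and counts discordant labels. In the version without week 6, at least 78% of those participants are less than 10 points above baseline at the trigger, so most of it is ordinary fluctuation or a return after a dip.

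**What to change.** In 14.1 and Appendix 1 item 2.3, let the 10-point limb run from the previous therapy session or the previous follow-up, with baseline as the comparator for week 6. Use the same comparator in item 5.2, which does not say what week 6 is compared with. For each event, log which limb was met and the change from baseline, so that deterioration can be told from recovery after a dip. Item 5.1.2 can stay as it is, since it belongs to the therapy track.

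The cost is a phrase in two places and a clarification in a third. Contacts do not rise at weeks 12 and 20, because 5.2 already requires them. At week 6 they rise only if 5.2 was not already read against baseline. More adverse events will be logged: in the illustration, 4–26 more waiting-list participants with at least one, or 6–29 with week 6, many through ordinary fluctuation.

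The change does not fully equalise ascertainment. The intervention arm is still screened at its three to four therapy sessions during the 20 weeks, and the waiting list is not.
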